#### Outcome measures:

Outcome measures will be: change in size of lesions before and after vaccination; incidence, time and size of recurrent disease; change in HPV type specific antibody titres before and after vaccination; change in prevalence of vaccine types HPV DNA on the cervix before and after vaccination; and change in prevalence of vaccine types HPV DNA in the warts after vaccination.

#### **4. DATA COLLECTION AND HANDLING**

Data will be collected prospectively as described above. Hand drawings of the affected areas will be made at each visit (see Appendix B diagram). In addition, a standardised photograph will be taken of the vulvo-vaginal area for future comparison. The lesion diameters will be measured and noted. Data sheets will be used to collect all clinical and laboratory results. Data entry into a designed data base will be done from 12 months onwards until all patients have completed a follow up period.

Analysis will be done of the pre-and post-vaccination antibody levels, immune status and HIV status and comparison of the above measures with the HPV and HPV-associated disease outcomes will be made.

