It is anticipated that the additional stimulation from a vaccine against the common wart-inducing HPV types (6 and 11) can help increase the production of protective antibodies in these susceptible women and can contribute to control the disease. In this prospective randomized trial, women with extensive genital warts will be studied, comparing those who have received quadrivalent HPV vaccine to a control group of women who have received hepatitis B vaccine.

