#### Inclusion criteria:

- Female patient > 16 years
- Presence of problematic vulvo vaginal genital warts:
  - Largest tumour diameter > 3 cm
  - OR      Tumour on labia minora and labia majora OR bilateral > 1 cm each side
  - OR      Tumour in vagina/cervix as well as on vulva > 1 cm lesion each
- HIV negative
- HIV infected:
  - CD4  $\geq 300 \times 10^6$  cells/l
  - OR      viral load controlled
  - OR      ARV compliant > 6 months

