#### Recruitment:

Women with genital warts will be evaluated for inclusion into the study. Those who fit the inclusion criteria and are without any of the exclusion criteria will be fully informed and invited to participate.

The first target will be to recruit the first fifty consecutive eligible patients who have signed written consent; recruitment for the study will be done for at least 24 months.

First clinical visit:

- Evaluation genital lesions:  
On study entry tumour size and position will be documented graphically (see Appendix B diagram) and photographically and viral typing from the vulva wart and cervix will be done using Roche LA test.
- Evaluation immune status:  
HIV status and CD4/CD8 count will be recorded and tested and the serum will be collected for antibody testing. Cervical disease of clinical significance will be excluded or treatment offered if relevant.
- Randomization:  
Patients will be randomized to receive either HPV4 or Hepatitis B vaccine.
- Vaccination:  
The participants assigned to the test group will be administered HPV4 vaccine in three doses as recommended by the manufacturer. Participants assigned to the control group will receive Hepatitis B vaccine in three doses as recommended by the manufacturer.

Follow-up clinical visits: week 8, week 16 and week 24:

- Evaluation genital lesions:  
Three follow up visits will be scheduled two months apart at which time the lesion size will be recorded.
- Evaluation immune status:  
After month 6 or the third visit, the serum will again be collected for antibody level testing.
- Treatment decision:  
According to the clinical response as measured at month six and onwards, locally destructive or surgical treatment will be allowed according to the preference of the clinician and as determined by clinical factors.

Follow up after treatment:

- Follow up will be done at six monthly intervals.
- Evaluation genital lesions:  
At these visits lesion size will be determined and documented. HPV typing on the cervical and vulval lesions will be repeated at least once.
- Further treatment of warts:  
If needed, repeat surgery and/or local destruction will be allowed and documented. These will be around week 48 and week 72, or study exit.

Study exit:

- Participants will exit the study in week 72.

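### Does the protocol fail to compare lesion size between the HPV4 and hepatitis B arms, and must it name the adjustment covariates?

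*Protocol*

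**What the plan says.** The Introduction describes a prospective randomised trial "comparing those who have received quadrivalent HPV vaccine to a control group of women who have received hepatitis B vaccine". The first-visit schedule (section 3, under Recruitment) repeats the design: "Patients will be randomized to receive either HPV4 or Hepatitis B vaccine". Both arms receive a three-dose course. The last hypothesis in section 2 is that HPV4 vaccination can reduce the size or recurrence of extensive warts after surgery.

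The Outcome measures list opens with "change in size of lesions before and after vaccination". It goes on to recurrence, antibody titres and vaccine-type HPV DNA on the cervix and in the warts. No item names an arm.

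Section 4 contains the only sentence on how outcomes will be analysed. Antibody levels before and after vaccination are to be analysed, "immune status and HIV status and comparison of the above measures with the HPV and HPV-associated disease outcomes will be made".

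The first visit supplies the candidate covariates: "On study entry tumour size and position will be documented graphically" and "HIV status and CD4/CD8 count will be recorded and tested". The second serum sample comes later: "After month 6 or the third visit, the serum will again be collected for antibody level testing". Entry is by any one of three lesion criteria. One is "Largest tumour diameter > 3 cm"; the others admit lesions of more than 1 cm at each of two locations, or warts on both labia minora and majora.

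**The concern.** Three features invite the criticism.

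- Both arms are vaccinated, so a change before and after vaccination can be computed in either arm without reference to the other. Women enter because their warts are large, so some shrinkage through regression to the mean is plausible in both arms. A before-after test in the HPV4 arm could then be significant with no vaccine effect.
- The one analysis sentence relates antibody level, immune status and HIV status to disease. Antibody level is measured after randomisation and depends on the vaccine given, and immune status may influence both antibody and warts. Such an association is not randomised evidence. The main hypothesis in section 2 runs through the antibody response, so a reader could mistake it for that.
- Starting size varies widely and there are only fifty women. Leaving recorded baseline size and HIV status out of the arm comparison would waste precision.

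At stake would be whether the trial's conclusion rests on its randomisation, and how much power fifty women provide.

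**Working it through.** **1. Is the arm comparison in the protocol?**

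| Place | What it fixes |
|---|---|
| Introduction | the trial compares HPV4 with hepatitis B vaccine |
| First-visit schedule | women are randomised to those two arms |
| Section 2, last hypothesis | HPV4 vaccination bears on wart size and recurrence |
| Outcome measures | what is measured on each woman |
| Section 4 | an additional analysis of antibody, immune and HIV status against disease |

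The first three rows give the contrast and attach HPV4 to lesion size, although the hypothesis is worded for the period after surgery. The fourth row defines variables. Change in size is one number per woman, it exists in both arms because both have a vaccination course, and it can be compared between arms. The fifth row adds an analysis. It contains no wording that replaces the comparison in the first row, and it does not say that the antibody association will serve as proof of efficacy.

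**2. What would a before-after test do?**

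Assume 25 women in the HPV4 arm, a two-sided 5% paired t test, and equal shrinkage in both arms of 0.3, 0.5 or 0.8 SD of the change. The test is then significant with probability 30%, 67% or 97%, while a between-arm test stays at 5%. The danger would be real if such a test were planned, but the protocol plans none.

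**3. What would covariate adjustment gain?**

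The protocol gives only the total of 50. Assumed are a 1:1 split, two-sided 5%, 80% power, equal variances at both times, and baseline correlation r of 0.3, 0.5 or 0.7. There is no stated power calculation to reproduce.

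- Variance of a change score: 2(1 − r) = 1.40, 1.00, 0.60.
- Variance after baseline adjustment: 1 − r² = 0.91, 0.75, 0.51.
- Ratio: (1 + r)/2 = 0.65, 0.75, 0.85.

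With 25 per arm the noncentral t (48 df) gives a detectable difference of 0.809 for unit SD.

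- Change score: 0.809 × √1.40, √1.00, √0.60 = 0.957, 0.809, 0.626 SD.
- Adjusted, before covariate cost: 0.809 × √0.91, √0.75, √0.51 = about 0.77, 0.70, 0.58 SD.
- Adjusted, with 46 df and variance inflation 1 + 2/45 = 1.044: 0.789, 0.716, 0.591 SD.

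The arithmetic is sound, but its starting line is an unadjusted change-score test, which appears nowhere in the protocol.

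**4. How firm is the gain?**

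Let s be follow-up SD divided by baseline SD. The change-score variance is 1 + s² − 2rs and the adjusted variance is s²(1 − r²). The difference is

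1 − 2rs + r²s² = (1 − rs)².

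With s = 1 this is 0.49, 0.25 or 0.09, matching step 3 (1.40 − 0.91, 1.00 − 0.75, 0.60 − 0.51). With r = 0.7 and s = 1.43, rs is about 1 and the gain vanishes, leaving only the cost of two degrees of freedom. With s below 1 it can be larger than shown. The protocol gives neither r nor s.

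**5. Does chance baseline imbalance make the unadjusted comparison invalid?**

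One standard error of the baseline difference is √(2/25) = 0.283 SD. It shifts an unadjusted change comparison by (1 − r) × 0.283 = 0.198, 0.141 or 0.085 SD. Over repeated randomisation this is noise already counted in the standard error. In simulation (20,000 trials per setting) rejection under no effect was 4.8% to 5.3% for both the unadjusted and the adjusted test. Adjustment is a matter of efficiency, not validity.

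**The case for a change.** The strongest case is that the protocol does state an analysis, and the one it states is an association rather than the randomised comparison. An author of the analysis plan who worked only from Outcome measures and section 4 could write before-after tests and antibody correlations and claim to have followed them. The remedy would be two sentences and no new data.

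Part of this stands. A sentence tying the lesion-size outcome to the arms would make the protocol clearer. Adjusting for baseline size is good practice, and keeping the antibody association apart from the randomised evidence is sensible.

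The rest does not stand. An analysis plan with no arm comparison would not follow the protocol, because it would ignore the Introduction and the randomisation. The choice of covariates and the exploratory label are normal content of an analysis plan, so their absence here is not an error. Nor would the two sentences complete the analysis. Size is measured at weeks 8, 16 and 24 and again later, and other wart treatment is allowed from month six, so a time point is also needed. An antibody model adjusted for HIV status and CD4 but not for arm would still mix the vaccine assigned with the antibody level it produces.

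**Conclusion.** No error. The HPV4 versus hepatitis B comparison is stated, it is backed by randomisation, and neither the outcome list nor section 4 contradicts it. The antibody analysis is additional and is not presented as evidence of efficacy. What remains is a preference about covariates and labels that an analysis plan can settle.

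The possible precision gain is about 0.17, 0.09 or 0.04 SD in the detectable difference (0.957 − 0.789, 0.809 − 0.716, 0.626 − 0.591). It rests on an assumed 1:1 split, two-sided 5%, 80% power, equal variances and r of 0.3 to 0.7, none of which the protocol gives. It describes what a good analysis plan could achieve. The conclusion itself rests on reading the Introduction, section 2, the visit schedule and section 4 together, and does not depend on those assumed values.

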#### **5. ETHICAL CONSIDERATIONS**

The study protocol will be submitted for approval to the relevant ethics committee. Participation in this study is completely voluntary.

All participants will receive written information about the study which they may retain, and will give written consent to participate prior to study entry. Patients undergoing treatment will be informed and will give previous written informed consent as per standard protocol of the treatment facility.

#### **6. COLLABORATION**

This study will be performed in collaboration with the VACCS consortium – colleagues from the Universities of Pretoria and Stellenbosch.

#### **7. BUDGET AND FUNDING**

The preliminary budget for this investigator initiated study is attached. Vaccine donations will be sought. The investigators have applied for funding at various funding bodies and are awaiting the evaluation results.

## **8. RESEARCH REPORTING**

The research analysis and reporting will be done independently from all sponsoring groups, but all collaborating parties will be invited to comment and approve manuscripts before final submission. Authorship of any resulting manuscript will follow Vancouver guidelines for contribution and intellectual input. Any conflict of interest and contribution to funding will be reported in all research output from this trial. The results will be reported and submitted to appropriate national and international forums and publications.

